Intervention:	Participants will be randomised to either no phototherapy or narrow band UVB phototherapy, 3 times per week for 8 weeks. All participants will wear a UVB dosimeter.
No. Subjects:	60 CIS patients from Perth, Western Australia, and surrounding districts. There will be 2 groups of healthy individuals of similar age and sex recruited in Perth. The first group includes 10 healthy

	individuals donating blood monthly for 12 months for biomarker analysis. At recruitment, these individuals will have no known autoimmune disease and have not had a cold, flu or other illness in the last 7 days. They will not be taking strong immunomodulatory drugs. Measurement of biomarkers of these healthy controls from the same location as the CIS patients will allow precise comparison of the relative extent of change in biomarker expression by UVB phototherapy.
	Another group of up to 40 healthy individuals of similar age and sex in Perth will be invited to donate blood on a single occasion for analysis of their blood cells. These individuals will have no known autoimmune disease and have not had a cold, flu or other illness in the last 7 days. They will not be taking strong immunomodulatory drugs. Measurement and characterisation of blood cells from these healthy controls from the same location as the CIS patients will allow comparison of cell changes related to the clinical condition of the CIS patients when first diagnosed.
Study Duration:	Recruitment will occur all year round in Perth. Participants will participate for one year.
	punterpute for one year.
Objectives of the Study:	To test the hypothesis that narrow band UVB phototherapy compared with no phototherapy, is associated with a decreased risk of developing Multiple Sclerosis over 12 months following a first demyelinating event.
Aims	 To determine the efficacy of narrow band UVB phototherapy in reducing the risk of recurrent disease activity (clinical demyelinating event or MRI activity) in the 12 months following onset of a first demyelinating event. To assess whether narrow band UVB phototherapy affects the clinical and/or radiological responses in high-risk CIS participants associated with development of Multiple Sclerosis. To determine whether narrow band UVB phototherapy alters the phenotype, function and transcriptional profile of immune cells in blood drawn 1 week, and 1, 2, 3, 6 and 12 months after initiation of phototherapy in comparison with those in blood taken immediately before phototherapy. To examine whether narrow band UVB phototherapy reduces immunological biomarkers in blood that have been associated with active Multiple Sclerosis. To determine if narrow band UVB phototherapy has an

	acceptable side effect and safety profile and is an acceptable treatment option for CIS patients.
Study Endpoints: (Primary and Secondary):	 Primary: Phototherapy-associated changes in transcriptome profiling in whole blood Phototherapy-associated changes in the phenotype of cells in freshly isolated peripheral blood Phototherapy-associated changes in T regulatory cells in the peripheral blood as measured by Foxp3 expression and by Foxp3 demethylation analysis Phototherapy-associated changes to immunological function of cells in the peripheral blood Development of a new demyelinating event defined as either A confirmed clinical relapse or A new cerebral T2 lesion and/or newly Gadolinium-enhancing cerebral lesion at either the 6 month or 12 month MRI scan compared to the study baseline scan. Secondary: Baseline to 12 month EDSS change Baseline to 12 month change in SF36v2 Quality of life score Baseline to 12 month creebral MRI grey matter volume change Baseline to 12 month cerebral MRI white matter volume change Safety: Adverse Events (including SAE) reported for narrow band UVB phototherapy
Study Design:	Participants will be randomised to treatment, or not, with narrow band UVB phototherapy. During the first 8 weeks (whether receiving phototherapy or not), all participants will wear a UVB dosimeter to measure their background environmental UVB exposure.
Eligibility Criteria:	 Aged between 18 and 65 years old inclusive. Recently diagnosed (within 120 days) with a first isolated, well-defined, uni- or multi-focal first demyelinating event (FDE).

- Able to receive their first phototherapy within 120 days of FDE symptom onset.
- An MRI brain scan that is supportive of demyelinating disease (Paty A or Paty B criteria, i.e. the presence of at least four T2 lesions greater than 3 mm, or at least three T2 lesions greater than 3 mm, one of which must be periventricular, respectively).
- An EDSS between 0 6.5 (inclusive)
- Must be able to give informed consent and sign the informed consent form
- Must be able to comply with all study procedures, and attend 24 phototherapy sessions and centres for venepuncture on multiple occasions during and after phototherapy
- If female of child-bearing age, must be willing to use effective contraception
- Must be willing to avoid use of sunbeds
- Must be able to stand in the phototherapy cubicle for up to 5 minutes at a time

Exclusion Criteria

- Known co-morbid illnesses that might be exacerbated by phototherapy, including lupus erythematosus and xeroderma pigmentosum
- A history of melanoma, multiple non melanoma skin cancers
- Previous prolonged courses of UVB or photochemotherapy (PUVA), or use of sunbeds
- Cardiovascular or respiratory disease that would prevent standing in the treatment cubicle
- Bullous disease
- Use of photosensitizing medications
- Very fair skin that burns with very minimal sun exposure (as judged by the dermatologist involved)
- Planning on becoming pregnant or breast feeding a child
- Current immunosuppressive drug therapy (beta-interferon, glatiramer acetate, natalizumab, mitoxantrone, or other chemotherapy agent specifically for demyelinating disease) prior to CIS diagnosis. (*Note that requirement for immunomodulatory therapy in the course of MS disease management will not exclude patients during follow-up; treatment variables will be collected and analysed in both the intervention and control arms in the planned analysis).
- Current pregnancy, breastfeeding or planning to become pregnant in the next 12 months.
- A second clinical demyelinating event prior to randomisation

	 Concurrent diagnosis of other neurological, psychiatric or other disease, which, in the opinion of the investigator, could impair capacity to provide informed consent or interfere with study compliance. Current enrolment in another interventional trial Any contraindication to MRI scanning or intravenous Gadolinium including: Cardiac Pacemaker Cardiac Defibrillator Metal fragments in the eye Any other non-MRI compatible medical device/implant or medical condition Previous allergic reaction to Gadolinium Severe claustrophobia
Study Procedures:	 As per Study Schedule in Appendix 1: Treatment schedule of phototherapy for 8 weeks and biomarker monitoring for 12 months from date of starting phototherapy Screening Questionnaire covering inclusion/exclusion criteria Blood collection for safety and laboratory parameters Saliva collection for Epstein Barr Virus (EBV) analysis Neurological reviews (including EDSS) Imaging: Best standard of care MRI Vital signs and physical examination, anthropometric measures, blood pressure Kurtzke Function System (KFS), Multiple Sclerosis Functional Composite Evaluation (MSFC) Quality of Life Questionnaires (SF36v2) Fatigue Severity Scale (FSS) Lifestyle Questionnaires (Baseline, Serial and Exit) Spectrophometric reading of skin UV reflectance, silicone cast of the back of the hand
Safety Parameters/analysis:	Adverse Events
Laboratory Parameters/Analysis:	As per Study Schedule in Appendix 1 Blood collection for Transcriptome analysis of cells in whole blood Analysis of cell populations in fresh non-coagulated blood Serum for 25(OH)D levels

Total Blood Volume:	 Isolation of peripheral blood mononuclear cells from noncoagulated freshly-taken blood for analysis of cell function and storage for further biomarker analysis DNA extracted from peripheral blood cells RNA extracted from peripheral blood cells Saliva collection for EBV analysis. At screening, blood and urine for pregnancy testing. 50 ml at screening/baseline visit prior to phototherapy and each study visit after the commencement of phototherapy (n=7) to a maximum of 360 ml over the entire study. For the additional group of 10 age and sex matched healthy individuals in Perth donating blood monthly for biomarker analysis, 11 ml blood will be collected monthly for biomarker analysis. The healthy control participants will be required to fill out the lifestyle questionnaires (see Appendix) at the beginning of the study, then again at the 6 and 12 month visits. For the additional group of up to 40 age and sex matched healthy individuals in Perth donating a single blood sample for cell isolation and characterisation, up to 45 ml blood will be taken.
Imaging Parameters/Analysis:	Best standard of care MRI as per Study Schedule in Appendix 1.
Sample Size Determination:	Our power calculations assume recruitment of 30 subjects to receive UVB phototherapy and 30 patients to not receive phototherapy (but allow study of seasonal effects). If new MRI lesions are expected in 90% of CIS patients over 1.5-2 years (CHAMPS, ETOMS, BENEFIT, PRECISE studies), then a treatment effect (ie reduction of 10%) should be discernible with a sample size of 30 patients. Power calculations for analysis of a biomarker (transcriptome) change based on standard deviation and means for each gene in winter indicated that between 11 and 27 patients need to be compared for a P<0.05.
Statistical Analyses:	Participants who have undergone 2 weeks (6 sessions) of narrow band UVB phototherapy will qualify for intention-to-treat analysis.

Differences in continuous responses between groups will be tested for significance using one-way ANOVA/t-tests or Kruskal-Wallis/Mann-Whitney tests as appropriate to the characteristics of the data. Covariate adjustment will be accommodated via general linear models. Comparisons of binary or categorical variables will be based on Fisher exact or Chi-squared tests, or logistical regression models to incorporate covariate adjustment. Repeated measurements over time will be analysed by longitudinal mixed models.

5. Introduction

Executive Summary

Several trials internationally are testing vitamin D supplementation as a modulatory therapy for Multiple Sclerosis. In Australia, the PrevANZ study (including Professors [name] and [name] on the steering committee) is testing whether vitamin D supplementation can slow or prevent progression to clinically definite MS in patients presenting with Clinically Isolated Syndrome (CIS). In this application (the PhoCIS trial, Phototherapy for CIS patients) we aim to examine the effects of narrow band UVB therapy on immune and inflammatory markers of disease, MRI and a unique transcription signature for MS, in patients with CIS. They are not on complicating therapy as yet and are ideal candidates for our trial. The intervention will be very similar to that given to patients with another autoimmune disease, namely psoriasis, where narrow band UVB phototherapy has proven safe and efficacious [1,2]. We anticipate that the intervention should give the patients not only the benefits of UV-induced vitamin D production but also the benefits of the other biological pathways stimulated in skin by UVB exposure [3-9].

This study has been funded as an NHMRC Project Grant, ID 1067209, for 2014-2016. This is a randomised controlled trial to assess the efficacy of narrow band UVB phototherapy to prevent or reduce the progression of patients with CIS (participants with a first demyelinating event, FDE) from development of MS. After agreeing to participate, participants will be randomly assigned to receive, or not receive, narrow band UVB phototherapy for 8 weeks and their biomarkers studied for a total of 12 months.

We will enroll 60 participants with CIS in Perth and surrounding districts. There will be an extra group of 10 age and sex matched healthy individuals recruited in Perth to donate blood monthly for biomarker analysis in their blood. Measurement of biomarkers of these healthy controls from the same city as the CIS patients will allow precise comparison of the relative extent of change in biomarker expression by UVB phototherapy.

Hypothesis to be tested:

Narrow band UVB phototherapy will benefit patients with CIS; it will alter in a sustainable manner the immunological biomarkers in blood that are associated with subsequent transition to clinically-definite MS. Narrow band UVB phototherapy will increase the ratio of regulatory to effector T lymphocytes, reduce the functional capacity of circulating dendritic cells (DCs), and ensure that the transcriptional profile in their peripheral blood mononuclear cells is similar to one associated with healthy controls and not one characterised for MS patients.

6. Background

Multiple Sclerosis (MS) is a progressive incurable immune mediated disease of the central nervous system that affects ~21,000 Australians. Both genetic and environmental factors contribute to disease risk, largely through effects on immune pathways [10,11]. Increasing MS incidence, prevalence and mortality with increasing latitude, and association of MS risk in observational studies with past sun exposure [12-15], has led to a focus on vitamin D as a major risk factor. However, studies in humans and mice by us and others [reviewed in (3-5)] suggest that immunoregulation by UV radiation is by both vitamin D-dependent and vitamin D-independent pathways. Our epidemiological work [16,17] indicates that vitamin D and sun exposure are additive independent risk factors for MS development. A Swedish study supports these findings [18]. Further, direct effects of sun exposure on MRI measures of neurodegeneration in MS, independently of vitamin D, have been reported [19].

- 6.1 Genes and immunological basis of MS. Recent genome wide association studies (GWAS) have implicated genes involved in homeostatic regulation of T cell-dependent immune activation and effector functions versus regulatory (immunosuppressive) immune responses [1,20]. These data have reinforced the view that T cell activation is a fundamental feature of MS pathogenesis. There is now evidence that this immunological 'signature' can be detected and monitored in peripheral blood samples [10,11,21-23]. Importantly for this application, disease-relevant blood biomarkers have been identified and independently validated in large cohort studies, including novel transcriptome signatures that have been incorporated into this research project.
- 6.2 Systemic immunomodulation by UV irradiation of skin. The immunomodulatory effects of UV radiation were first observed in the 1970s [24], with the demonstration that after transplantation of a UV-induced skin tumour onto a UV-irradiated mouse the tumour grew; while the tumour was immunologically destroyed by a naïve mouse. This systemic immune-suppressing effect of UV exposure has been extensively demonstrated in humans [25, 8]. Human and murine studies suggest a prominent role in UV-induced immune suppression for DCs and induced Treg [5,26-29], and reduced memory T cell responses [30]. Several chromophores in skin for UVB photons have been implicated [31-34]. All may initiate pathways involved in signalling from skin

to immune cells in draining lymph nodes, and tissues beyond. Importantly for this study proposal, sub-erythemal amounts of UVR in humans can suppress both local and systemic immunity, measured functionally in terms of reduced cell-mediated immune responses. Recent studies by the investigators using chimeric mice engrafted with bone marrow from UV-irradiated mice, suggest that UV irradiation of skin alters the differentiation program of myeloid progenitors in bone marrow so terminally differentiated DCs and macrophages are less immunogenic and more regulatory [28,35]. Importantly, the effect of suberythemal UVR to skin on bone marrow myeloid cell progenitors is by a vitamin D-independent, prostaglandin E₂ (PGE₂)-dependent process. As recently published [35-38], our data suggest that epigenetic modification of an early myeloid progenitor in the bone marrow is involved. We propose that in patients with CIS, exposure to narrow band UVB will similarly alter the immunogenic properties of circulating DCs towards a regulatory profile.

- 6.3 Identification of MS biomarkers: transcriptional and immunophenotyping profiles. MS and its preclinical condition CIS are caused, at least in part, by pathogenic leukocytes that transit from lymphoid tissue to the brain via the peripheral circulation, with measurable changes in gene expression profiles in peripheral blood mononuclear cells associated with disease activity [39]. This paradigm is supported by studies on genetic susceptibility: most genes identified so far as associated with MS are primarily expressed in immune cells, especially involving the DC/T cell axis [10]. In the context of this proposal, recent advances by Investigator [name] and colleagues have identified specific transcriptional signatures associated with MS, which are also modified in a seasonally-dependent manner [40].
- 6.4 The intervention, Narrow band UVB phototherapy. Narrow band UVB phototherapy is a routine treatment for patients with psoriasis. As for psoriasis patients, a Wayne Electronics, Series M.S.1, phototherapy cabinet with output (between wavelengths 311-312 nm) of 0.6 mW/cm² will be used. Phototherapy will be given three times/week for eight weeks (24 exposures in total). Phototherapy will be delivered according to the Dundee protocol which is based on the patient's skin type. The starting dose of 20 mJ/cm² is based on knowledge of the skin type and will be well below the likely erythema threshold. Patients start with 40% increments on their initial dose, which will be reduced to 20% increments after 6 exposures. At each visit the dose given and any adverse effects will be recorded.

All participants will wear a calibrated UVB dosimeter (Scienterra Limited, Otago New Zealand). This will measure their UVB (as in sunlight) exposure. The UVB dosimeter is the size of a watch and is worn around the wrist. The dosimeter will collect daily UVB exposure data. The dosimeters will not be worn in the photobooth.

6.5 Known and potential risks and benefits of UVB phototherapy, if any, to human participants. Psoriasis has been successfully treated using narrow band UVB (TL-01) lamps with a 311 nm peak emission [1,2]. No increase in oncogenic risk for narrow band UVB phototherapy has

been reported [2]. The face and eyes are protected during sessions of otherwise total body irradiation. Multiple mechanisms are involved in the control of psoriasis by narrow band UVB, including reduced inflammatory DCs infiltrating the skin [41], increased regulatory T cell number and function [8] and modulation of the IL-17/IL-23 axis [41].

A search of the literature has not revealed any studies of phototherapy for MS patients. There was one study of extracorporeal photochemotherapy used in 5 patients with refractory Relapsing Remitting MS with some success [42]. Phototherapy for MS patients is also supported by demonstration that UVR can suppress the severity of experimental autoimmune encephalomyelitis (a murine model of MS) when there were minimal changes in serum 25(OH)D levels [43].

This trial of narrow band UVB phototherapy will be documented in compliance with the protocol, GCP and the applicable regulatory requirements.

Description of the population to be studied. Patients at high risk of MS [patients with CIS defined by a First Demyelinating Event (FDE)].

7. Hypothesis, Aims and Objectives

Hypothesis: Narrow band UVB phototherapy will benefit patients with CIS; it will alter in a sustainable manner the immunological biomarkers in blood that are associated with subsequent transition to clinically-definite MS. UVB phototherapy will increase the ratio of regulatory to effector T lymphocytes, reduce the functional capacity of circulating dendritic cells (DCs), and ensure that the transcriptional profile in their peripheral blood mononuclear cells is similar to one associated with healthy controls and not one characterised for MS patients.

Aims and Objectives of the PhoCIS trial: In 30 patients with CIS given a course of narrow band UVB phototherapy (3 exposures/week for 8 weeks) and 30 CIS patients without phototherapy wearing UVB dosimeters, we will examine whether:

- 1. UVB phototherapy reduces the risk of a recurrent disease activity (clinical demyelinating event or MRI activity) in the 12 months following onset of a first demyelinating event.
- 2. UVB phototherapy affects the clinical and/or radiological responses associated with development of MS in high-risk CIS participants.
- 3. UVB phototherapy alters the phenotype, function and transcriptional profile of immune cells in blood drawn 1 week, and 1, 2, 3, 6 and 12 months after initiation of phototherapy in comparison with those in blood taken immediately before phototherapy.
- 4. UVB phototherapy reduces immunological biomarkers in blood that have been associated with active MS.
- 5. UVB phototherapy is a safe and acceptable treatment option for CIS patients.

8. Methodology

8.1 Participants in the PhoCIS Trial

We will recruit 60 patients who have had a first demyelinating event (i.e. diagnosed with CIS). Of these, 30 will receive phototherapy in addition to standard-of-care, while the remaining 30 will receive standard-of-care treatment. All participants will wear a UVB dosimeter.

As part of standard-of-care, all patients will receive sufficient vitamin D supplementation to achieve serum 25(OH) D levels of ≥ 100 nmol/L.

Patients with CIS will be approached by Professors [name] or [name] to join the trial.

There will be two additional groups donating blood. In the first group, 10 age and sex matched healthy individuals in Perth will donate 11 ml blood monthly for 12 months for selected biomarker analysis (transcriptome analysis of cells in whole blood and serum 25(OH)D levels). Measurement of these particular biomarkers of these healthy controls from the same city as the CIS patients will allow precise comparison of the relative extent of change in expression of those biomarkers by UVB phototherapy, and during the different seasons of the year. Additionally, this group of healthy controls will be required to fill out the lifestyle questionnaires (see Appendix) at the beginning of the study, then again at the 6 and 12 month visits. The healthy individuals donating blood monthly for 12 months will be recruited by advertisement from the staff at the Telethon Kids Institute in Subiaco, Western Australia. They will not be paid.

In the second group, up to 40 age and sex matched healthy individuals in Perth will donate up to 45 ml blood on a single occasion. The profile of their cells will be compared with those from blood taken from the study participants with CIS at baseline. They will not be paid.

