For the additional group of up to 40 age and sex matched healthy individuals in Perth donating a single blood sample for cell isolation and characterisation, up to 45 ml blood will be taken. At the time of their recruitment by advertisement at the Telethon Kids Institute, these individuals will have no known autoimmune disease and have not had a cold, flu or other illness in the last 7 days. They will not be taking strong immunomodulatory drugs (the taking of agents such as vitamin D, NSAIDs or paracetamol will be permitted). The profile of the cells in the blood of the healthy individuals will be compared with that of the CIS participants at baseline.

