19.4.2 Temporal patterns between biomarker measures and relapse

Blood will be taken at baseline, 1 week, 1 month, 2 months, 3 months, 6 months and 12 months after initiation of UVB phototherapy. Other than immunophenotyping of cells in freshly collected blood, all other preparations of blood, serum and peripheral blood mononuclear cells will be frozen and analysed at the end of the study. Differences in continuous responses between groups will be tested for significance using one-way ANOVA/t-tests or Kruskal-Wallis/Mann-Whitney tests as appropriate to the characteristics of the data. Covariate adjustment will be accommodated via general linear models. Comparisons of binary or categorical variables will be based on Fisher exact or Chi-squared tests, or logistical regression models to incorporate covariate adjustment. Repeated measurements over time will be analysed by longitudinal mixed models.

20. Data Management

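### The single-draw healthy donors are matched to CIS patients on age and sex but not on calendar period, so season or run date could mix with the CIS-versus-healthy difference

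*Protocol*

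**What the plan says.** Section 8.1 sets up a second healthy group: "up to 40 age and sex matched healthy individuals in Perth will donate up to 45 ml blood on a single occasion". Its use follows: "The profile of their cells will be compared with those from blood taken from the study participants with CIS at baseline". The synopsis gives the purpose, saying that measuring these donors "will allow comparison of cell changes related to the clinical condition of the CIS patients when first diagnosed".

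Age and sex are the only matching factors. The remaining donor conditions in section 9 concern health, medication and place, for example that "these individuals will have no known autoimmune disease and have not had a cold, flu or other illness in the last 7 days". None concerns the date or season of the draw.

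On the CIS side, the synopsis says recruitment runs throughout the year, and section 9 invites patients presenting in 2014, 2015 and 2016. Section 10.3.1, in contrast, says the trial is performed in winter.

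On assay timing, section 19.4.2 says: "Other than immunophenotyping of cells in freshly collected blood, all other preparations of blood, serum and peripheral blood mononuclear cells will be frozen", with analysis at the end of the study. On season, section 6.3 says of MS transcriptional signatures that they are ones "which are also modified in a seasonally-dependent manner". The other healthy group, 10 people bled monthly for 12 months, is partly intended to cover the seasons. Sections 8.1 and 10.6 limit its measurements to the whole-blood transcriptome and serum 25(OH)D.

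**The concern.** A comparison of patients with healthy people at one time point is observational. It supports a statement about disease only if the two groups are alike in other things that move the marker. Two calendar factors are left open here.

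- **Season of draw.** This can act on any cell measure, whenever the assay is run.
- **Run date.** This acts on fresh immunophenotyping, the one assay in section 19.4.2 that is not held back to the end of the study. Drift in instrument or reagents over three years would enter the comparison wherever donor and patient dates differ.

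The protocol takes season seriously elsewhere, but its seasonal reference group is not measured for cell phenotype and so does not serve this comparison. If the 40 donors happened to be bled in a narrow part of the recruitment period, a calendar effect could be reported as a feature of CIS at first diagnosis.

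**Working it through.** The protocol states no sample size, effect size or power for this comparison, so there is no figure to reproduce. The check below illustrates how much calendar imbalance could matter.

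**Inputs from the protocol.** 60 CIS patients and up to 40 donors (section 8.1), taken as 60 and 40. Significance level 0.05: this is given in section 19.3 for the transcriptome calculation only, and is assumed here to apply and to be two-sided.

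**Assumed inputs.** Two periods (seasons or run periods) whose marker means differ by s = 0.2, 0.3 or 0.5 SD. CIS baselines split 50/50 between them in the first three scenarios. No true CIS effect. No adjustment.

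**Formula.** In SD units the standard error of the group difference is √(1/60 + 1/40) = 0.204. If a fraction f of donors and one half of CIS patients fall in the second period, the spurious difference is d = s × |f − 0.5|. If the two groups are in wholly different periods, d = s. The chance of a false positive is Φ(d/0.204 − 1.96) + Φ(−d/0.204 − 1.96).

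Example: s = 0.5 with all donors in one period gives d = 0.5 × 0.5 = 0.25, d/0.204 = 1.22 and a rate of 23.2%.

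| Donor draws | s = 0.2 | s = 0.3 | s = 0.5 |
|---|---|---|---|
| 50/50, as CIS | 5.0% | 5.0% | 5.0% |
| 75/25 | 5.7% | 6.6% | 9.4% |
| All in one period, CIS 50/50 | 7.8% | 11.4% | 23.2% |
| No overlap with CIS at all | 16.5% | 31.2% | 68.8% |

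The last row uses the normal approximation. A non-central t with 98 degrees of freedom gives 16.3%, 30.7% and 67.9%.

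**What adjustment can do.** Suppose all 40 donors fall in one period and k CIS patients share it. A model with group and period then compares those k patients with the 40 donors, with standard error √(1/k + 1/40):

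- k = 30: √(0.0333 + 0.025) = 0.24
- k = 15: √(0.0667 + 0.025) = 0.30
- k = 5: √(0.2 + 0.025) = 0.47
- k = 0: not estimable, because period and group are the same variable.

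So overlap keeps the test valid, at the price of a standard error that rises from 0.204 to between 0.24 and 0.47. With donors split 75/25 (30 and 10) and CIS 30 and 30, the price is small. The two within-period variances are 1/30 + 1/30 = 0.0667 and 1/30 + 1/10 = 0.1333, and combining them gives √(1/(15 + 7.5)) = 0.211.

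A simulation with 3,000 runs per setting, including a further shift of 0.8 SD, gave false-positive rates of 4.5% to 6.3% once a period term was included, whether donors were split 75/25 or all in one period. With donors and CIS in the same proportions it gave 3.6% to 4.6% without adjustment and 4.7% to 5.2% with it.

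**The case against.** The strongest reply is that the protocol is silent on when donors are bled, and silence is not an error. Appointment dates are operational, section 19.4.2 already allows covariate adjustment through general linear models, and naming the covariate is normally left to the SAP. The comparison is also in no stated aim or endpoint.

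Much of this stands, and it rules out several stronger readings that a reader might infer:

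- **That donors will be bled in a block.** Section 11 mentions posters at one institute. That makes a block possible, but no section says it.
- **That donor cells are known to be phenotyped fresh.** Section 9 speaks of cell isolation and characterisation. Fresh phenotyping is implied, not stated, and frozen preparations are analysed together at the end, so run date need not differ for them.
- **That the protocol says cell phenotype is seasonal.** The statement in section 6.3 is about transcription. Extending it to phenotype is an inference.
- **That a calendar difference can never be removed afterwards.** This is true only without overlap. If CIS baselines do accrue all year, some should share the donors' period, and a period term then works.
- **That 16%, 31% and 69% are the expected error rates.** They require wholly separate periods, which nothing in the protocol implies.

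What does not stand is leaving the matter to the SAP. The SAP can add a period term, but it cannot create overlapping draw dates. That is settled when donors are booked, and the matching rule in sections 8.1 and 9 is where it belongs.

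**Conclusion.** The point holds as a possible confounder left open by a stated matching rule, not as a demonstrated bias. Under the assumed shifts of 0.2 to 0.5 SD, moderate imbalance raises the per-marker false-positive rate from 5% to between 5.7% and 9.4%. Drawing all donors in one period raises it to between 7.8% and 23.2%. Only complete separation gives 16% to 69% and leaves the effect beyond repair. The sizes rest on assumed shifts, a two-period simplification, 40 donors actually recruited and a two-sided 0.05 test.

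The all-year and winter statements conflict and must be reconciled. Winter-only recruitment would narrow the season spread among CIS patients, but it would neither tie donor dates to theirs nor remove drift across years.

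This is an optional-to-moderate improvement to an auxiliary comparison. The randomised UVB comparison and the listed primary and secondary endpoints are not affected.

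**What to change.** In sections 8.1 and 9, add calendar period to the age and sex matching. Spread donor draws in parallel with CIS baseline visits, at about two donors for every three patients (40 to 60), in the same month or season where feasible. State whether donor cells are phenotyped fresh, and if so use the same cytometry settings as for the patients. Record draw date and run date for every sample, and include draw period in the CIS-versus-healthy model. Reconcile the synopsis with section 10.3.1 on the season of recruitment.

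The cost is time: donor sampling finishes only when CIS accrual does. No extra donors, blood or assays are needed.
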